13.6 Gold Standards for IFI Infections

The criteria established by the EORTC/MSG for proven or probable IFI IA will be used as the gold standard. These definitions have been used as the primary endpoints for prior studies validating the Fungitell beta-D-glucan Assay.

13.6.1 Methodology to Identify IFI:

The EORTC/MSG guidelines incorporate clinical, microbiologic, histopathologic, and radiographic data for classification of proven or probable IFI. Therefore, in order to establish these diagnoses, the following data will be obtained on the IFI checklist (Section 10.2): pathology reports (including autopsy reports), CT scan and MRI reports, fungal gram stain and microbiology culture results, non-culture mycology testing results (i.e. histoplasma urine antigens, cryptococcal CSF and serum antigens), ophthalmology exams, and bronchoscopy reports. An independent data review committee including infectious disease and oncology experts who are unaware of treatment assignments will review and classify all cases of fungal infection as proven, probable, or possible, according to the consensus criteria of the EORTC/MSG.

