To our knowledge BG testing is not routinely performed at many pediatric centers but may be performed at some of the COG sites. Regardless of the number of institutions offering such BG testing, we anticipate that such testing will be ordered by a subset of treating physicians. The local BG results will not be included in our final analysis of the biomarker assay's operating characteristics. However, these results may effect a change from fungal prophylaxis to preemptive or empiric therapy and may encourage or discourage more comprehensive efforts to diagnose a proven or probable IFI in any given patient. This in turn may falsely influence our evaluation of the Fungitell beta-D-glucan Assay's operating characteristics. For each patient we will identify whether local BG testing has been performed and, via a sensitivity analysis, explore whether such a practice influences the operating characteristics. The plans for this sensitivity analysis are described in more detail in Section 13.9.4 below.

The Fungitell beta-D-glucan Assay is reported in pg/ mL of patient's serum. The manufacturer recommendation for a single positive Fungitell Assay result of > 80 pg/mL will be used to define a positive test.

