Additionally, the ROC curves will be used in an exploratory analysis to identify the threshold for the biomarker assay that optimizes the diagnostic test's sensitivity while maintaining a reasonable specificity. The identified thresholds will be used to categorize each patient as "likely to have IFI" and "not likely to have IFI". Once these 2 sub-groups are defined we will calculate the incidence rates of IFI for each sub-group and compare them. Because the anticipated incidence for IFI may be variable between the two study

arms (those receiving an azole and those receiving caspofungin) this approach will have to be done at the level of each study arm. The incidence rates will be compared statistically using Pearson's Chi-square analysis.

Finally, to further explore the ideal utility and interpretation of each biomarker, serial testing results will be explored. For this analysis the Fungitell beta-D-glucan Assay will be considered positive when a patient has 2 consecutive test results ≥ 80 pg/mL. Operating characteristics and ROC curves will be constructed in a similar manner as discussed above.

13.9.4 Sensitivity Analysis:

Sensitivity analyses will be explored for the reasons expressed in Section 13.7.1 and 13.8. The first sensitivity analysis will attempt to identify the direction and magnitude of the bias resulting from the availability of clinical BG testing performed outside of the ancillary study. Such testing has the potential to change the treating clinician's approach for diagnosing an IFI. It is possible that these test results could result in more or less investigation (e.g. radiologic imaging) to identify an IFI, which could ultimately impact on the incidence of identified IFI. Therefore, in addition to calculating the operating characteristics for all patients enrolled, the same operating characteristics will be calculated after excluding all patients that had at least 1 biomarker test result available to the treating clinician.

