^d Recovery of *Aspergillus* species from blood cultures invariably represents contamination.

Criteria for probable invasive fungal disease except for endemic mycoses

Host factors^a

- Recent history of neutropenia ($< 0.5 \times 10^9$ neutrophils/L [< 500 neutrophils/mm³] for >10 days) temporally related to the onset of fungal disease
- Receipt of an allogeneic stem cell transplant
- Prolonged use of corticosteroids (excluding among patients with allergic bronchopulmonary aspergillosis) at a mean minimum dose of 0.3 mg/kg/day of prednisone equivalent for > 3 weeks
- Treatment with other recognized T cell immunosuppressants, such as cyclosporine, TNF- α blockers, specific monoclonal antibodies (such as alemtuzumab), or nucleoside analogues during the past 90 days
- Inherited severe immunodeficiency (such as chronic granulomatous disease or severe combined immunodeficiency)

Clinical criteria^b

Lower respiratory tract fungal disease^c

- The presence of 1 of the following 3 signs on CT:
 - Dense, well-circumscribed lesions(s) with or without a halo sign
 - Air-crescent sign
 - Cavity

Tracheobronchitis

- Tracheobronchial ulceration, nodule, pseudomembrane, plaque, or eschar seen on bronchoscopic analysis

Sinonasal infection

- Imaging showing sinusitis plus at least 1 of the following 3 signs:
 - Acute localized pain (including pain radiating to the eye)
 - Nasal ulcer with black eschar
 - Extension from the paranasal sinus across bony barriers, including into the orbit

CNS infection

- 1 of the following 2 signs:
 - Focal lesions on imaging
 - Meningeal enhancement on MRI or CT

Disseminated candidiasis^d

- At least 1 of the following 2 entities after an episode of candidemia within the previous 2 weeks:
 - Small, target-like abscesses (bull's-eye lesions) in liver or spleen
 - Progressive retinal exudates on ophthalmologic examination

Mycological criteria

Direct test (cytology, direct microscopy, or culture)

- Mold in sputum, bronchoalveolar lavage fluid, bronchial brush, or sinus aspirate samples, indicated by 1 of the following:
 - Presence of fungal elements indicating a mold
 - Recovery by culture of a mold (e.g., *Aspergillus*, *Fusarium*, *Zygomycetes*, or *Scedosporium* species)

Indirect tests (detection of antigen or cell-wall constituents)^e

- Aspergillosis
 - Galactomannan antigen detected in plasma, serum, bronchoalveolar lavage fluid, or CSF
- Invasive fungal disease other than cryptococcosis and zygomycoses

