 - β -D-glucan detected in serum

NOTE. Probable IFD requires the presence of a host factor, a clinical criterion, and a mycological criterion. Cases that meet the criteria for a host factor and a clinical criterion but for which mycological criteria are absent are considered possible IFD.

^a Host factors are not synonymous with risk factors and are characteristics by which individuals predisposed to invasive fungal diseases can be recognized. They are intended primarily to apply to patients given treatment for malignant disease and to recipients of allogeneic hematopoietic stem cell and solid-organ transplants. These host factors are also applicable to patients who receive corticosteroids and other T cell suppressants as well as to patients with primary immunodeficiencies.

^b Must be consistent with the mycological findings, if any, and must be temporally related to current episode.

^c Every reasonable attempt should be made to exclude an alternative etiology.

^d The presence of signs and symptoms consistent with sepsis syndrome indicates acute disseminated disease, whereas their absence denotes chronic disseminated disease.

^e These tests are primarily applicable to aspergillosis and candidiasis and are not useful in diagnosing infections due to *Cryptococcus* species or *Zygomycetes* (e.g., *Rhizopus*, *Mucor*, or *Absidia* species). Detection of nucleic acid is not included, because there are as yet no validated or standardized methods.

APPENDIX III: COG STEM CELL COMMITTEE CONSENSUS GUIDELINES FOR ESTABLISHING ORGAN STAGE AND OVERALL GRADE OF ACUTE GRAFT VERSUS HOST DISEASE (GVHD)

Reporting Requirements for Acute GVHD in COG Studies

In an attempt to standardize reporting of acute GVHD, the COG Stem Cell Transplantation Committee has adopted a modification of guidelines that were originally developed at the University of Michigan.

Table 1 outlines standard criteria for GVHD organ staging. However, confounding clinical syndromes (such as non-GVHD causes of hyperbilirubinemia) may make staging GVHD in a given organ difficult. In addition, timing of organ specific symptoms affects whether that symptom is more or less likely to be true GVHD. Please refer to **Tables 2 and 3** to assist you in deciding whether to attribute these clinical findings to GVHD, especially in situations where a biopsy is not possible. For additional help, please see the text which follows the tables.

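### The reference standard for the beta-D-glucan assay accepts serum beta-D-glucan as evidence of IFI, so a locally tested patient can become a case through the marker under evaluation

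*Combined protocol and SAP*

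**What the plan says.** Section 13.6 sets the reference standard for the assay: "The criteria established by the EORTC/MSG for proven or probable IFI IA will be used as the gold standard". Section 13.7.2 repeats the choice and gives comparability with other studies as a reason. Neither section makes an exception for beta-D-glucan.

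Appendix II reproduces the criteria. Among the indirect mycological tests it lists beta-"D-glucan detected in serum". The rule is: "Probable IFD requires the presence of a host factor, a clinical criterion, and a mycological criterion". Without mycology the patient drops a category: "Cases that meet the criteria for a host factor and a clinical criterion but for which mycological criteria are absent are considered possible IFD". One listed host factor is "Receipt of an allogeneic stem cell transplant", which every enrolled patient meets.

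On local testing, Section 13.5 states: "we anticipate that such testing will be ordered by a subset of treating physicians". It then says "The local BG results will not be included in our final analysis of the biomarker" assay's accuracy. That sentence concerns the index test and is silent on the reference standard. Study-run assays are batched and withheld from treating physicians.

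Section 13.9.4 plans a sensitivity analysis in which "the same operating characteristics will be calculated after excluding all patients that had at least 1 biomarker test result available to the treating clinician". The main analysis keeps all patients.

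On what the review committee sees, Section 9.3.2 says that everything relevant to the EORTC/MSG guidance is reviewed. The itemised lists in Sections 9.3.2, 10.2 and 13.6.1 name only histoplasma and cryptococcal antigens under non-culture mycology. Reviewers are blinded to antifungal exposure; blinding to beta-D-glucan is not mentioned.

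**The concern.** Take two children with the same qualifying CT lesion and no other mycology. The one with a positive local beta-D-glucan is probable and counts as a case. The other is possible and counts as a non-case. The marker has helped to decide who is diseased, and its accuracy is then measured against that decision. Keeping local results out of the index-test data does not take them out of the reference standard.

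At stake is the credibility of the accuracy estimates for exploratory objective 1.2.6, and in particular the hypothesis in Section 13.2 that sensitivity exceeds 90%. With so few expected cases, a handful defined by the marker can shift the result visibly. Section 13.10 expects the answer to influence later clinical use of the test, whichever way it falls.

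**Working it through.** **Inputs.** From Section 13.9.1: 400 patients, 200 per arm, IFI rates of 7% and 2%. From Section 13.1.3: pooled sensitivity 77% and specificity 85% from a meta-analysis, used only as illustrative true values. Assumed, because the documents give neither: k, the number of cases that are probable only through a local beta-D-glucan; and c, the probability that the study assay is also positive in such a case. The 70% starting value is likewise an assumption.

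**The plan's own figure.** 200 × 0.07 + 200 × 0.02 = 14 + 4 = 18 events, as in Table 3. (The printed pooled rate of 4.6% matches 26/560 from the parent trial's rounded counts; 18/400 is 4.5%. The difference is immaterial.) One case is worth 1/18 = 5.6 percentage points of sensitivity.

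**Illustration A: 18 cases in total, k of them defined by beta-D-glucan, c = 1.**
Apparent sensitivity = [s × (18 − k) + k] / 18.

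| True s in the other cases | k = 2 | k = 4 | k = 6 |
|---|---|---|---|
| 70% | 13.2/18 = 73.3% | 13.8/18 = 76.7% | 14.4/18 = 80.0% |
| 77% | 14.32/18 = 79.6% | 14.78/18 = 82.1% | 15.24/18 = 84.7% |

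**Illustration B: 18 independently established cases, plus k = 4 patients without IFI relabelled as cases.** At baseline, with s = 77% and specificity 85%, true positives are 18 × 0.77 = 13.86 and false positives are 382 × 0.15 = 57.3. Relabelling moves 4c positives from false to true. Cases become 22 and non-cases 378.

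| | Sensitivity | Specificity | PPV |
|---|---|---|---|
| Baseline, s = 77% | 77.0% | 85.0% | 13.86/71.16 = 19.5% |
| c = 1 | 17.86/22 = 81.2% | 1 − 53.3/378 = 85.9% | 17.86/71.16 = 25.1% |
| c = 0.8 | 17.06/22 = 77.5% | 1 − 54.1/378 = 85.7% | 17.06/71.16 = 24.0% |

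Starting instead from s = 90% (16.2 true positives), c = 0.8 gives (16.2 + 3.2)/22 = 88.2%, a fall. So sensitivity rises only when c exceeds s. Specificity and PPV rise in every case shown, specificity by less than one point and PPV by about five.

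**What the planned exclusion costs.** If 25% or 50% of cases were locally tested (assumption), 18 × 0.75 = 13.5 or 18 × 0.50 = 9 events remain. The loss includes locally tested patients whose IFI was proven by culture or biopsy and whose status never depended on the marker.

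**The case against.** Four points weigh on the other side.

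1. **The plan already has a remedy.** A reader might infer that the Section 13.9.4 analysis leaves incorporation untouched because its stated motive is altered diagnostic work-up. The documents do not support that. Whatever its motive, excluding every patient with a result available to the clinician sets k to zero for the local-testing route, and Section 13.5 commits to recording local testing for each patient. What remains is that the analysis is secondary and discards valid events.

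2. **The pathway is not established.** The committee data lists do not name beta-D-glucan. If they are complete, local results never reach the reviewers. But they also omit galactomannan, another Appendix II criterion, and the general statement in Section 9.3.2 is wider. The question is open in both directions.

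3. **The direction is conditional.** A reader might infer that sensitivity and specificity are both bound to be inflated, because such cases are near-certain true positives. The documents do not show this. Up to seven weekly samples, with one positive sufficient, favour agreement between assays. Against it, local tests are ordered at clinical discretion, outpatient draws happen only when possible, blood volume is capped, positives are retested, and the hypothesis counts only positives before diagnosis.

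4. **The effect may be small.** Section 13.5 says the test is not routine at many paediatric centres, and a yeast-positive blood culture is proven IFI without it, so k may be low. The shifts lie inside the exact 95% interval for a sample this size (16/18 = 88.9%, 65.3% to 98.6%), and none shown in Illustration A reaches 90%. This stands as a limit on importance. Wide random error does not, however, justify leaving in an avoidable systematic one.

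**Conclusion.** The circularity is in the rule as written: unmodified EORTC/MSG criteria admit the marker, local testing is expected, and no text keeps local results out of case classification. Beta-D-glucan alone does not make a case; a clinical criterion is also required, so the route is an upgrade from possible to probable.

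The likely effect is inflated specificity and PPV, with inflated sensitivity if agreement between the assays exceeds the true sensitivity. The size cannot be determined from the documents. The illustrative range for sensitivity is about 3 to 10 points for k = 2 to 6 with full agreement, and close to zero or slightly negative at 80% agreement. It rests on assumed k and c, and on local results reaching the committee.

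The point concerns an optional, exploratory aim and should be corrected in that aim's analysis. A reader might infer that it calls the treatment comparison into question; nothing in this argument does, since the circularity arises only when beta-D-glucan is itself the test being judged.

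**What to change.** For Section 13 only:

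- Make the main reference standard the committee's EORTC/MSG proven or probable classification with beta-D-glucan disregarded as a mycological criterion, and blind the committee to all beta-D-glucan results at that step.
- After that classification is recorded, flag on the central review form any case whose only mycological evidence is beta-D-glucan, and report the count.
- Report accuracy under the unrestricted classification as a sensitivity analysis, alongside the exclusion analysis already planned in Section 13.9.4.
- State in Sections 9.3.2 and 10.2 whether local beta-D-glucan results are submitted and at which step the committee sees them.

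Leave the parent trial's primary endpoint as it is.

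The cost is one form field, a two-step review and some SAP wording. There may be a few fewer reference cases. Some genuine IFIs supported only by beta-D-glucan would count as non-cases, so their positive tests would count as false positives and pull specificity down. Comparability with studies that used the unmodified criteria, which Section 13.7.2 values, is slightly reduced in the main result but preserved by the unrestricted sensitivity analysis. Unlike the exclusion analysis, this keeps locally tested patients whose IFI was established by other evidence.

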13.7 Justification of Methodologic Choices

13.7.1 Justification for Chosen Threshold for the Fungitell beta-D-glucan Assay:

IFI outcomes are often devastating; thus it is desirable to optimize sensitivity at the potential expense of specificity. Furthermore, a highly sensitive test will likely result in few false negatives. Clinicians caring for patients with positive tests would then have a heightened concern for IFI while a negative test result would reassure them that no further modifications to antifungal therapy are necessary at that time. It was with these intentions that the following threshold value was chosen to conclude negative and positive results.

The Fungitell beta-D-glucan Assay threshold result of ≥ 80 pg/mL was chosen based on manufacturer recommendations and available data. For two adult studies that evaluated this test, the cut-off for a positive test was lowered to > 60 pg/mL.^{63,64} Lowering of the manufacturer threshold in these two studies resulted in high sensitivity, which is consistent with the goals of our study. However, analysis of BG levels in 120 healthy children revealed that 22% of them had BG levels greater than 60 pg/mL.⁶⁶ Although this level would optimize sensitivity, the likelihood for false positivity is too high. There were still 15% of healthy children in this study that had a level of ≥ 80 pg/mL. This suggests that even at a level of ≥ 80 pg/mL, sensitivity of this assay in children would be preserved. Therefore, the manufacturer threshold of ≥ 80 pg/mL was chosen. A post hoc analysis of various cutoffs as well as assessment of sequential positive testing will be performed in an attempt to identify the most ideal cut-off for future use of this assay (please see statistical analysis below).

13.7.2 Justification for IFI Gold Standard:

We have chosen to use EORTC/MSG defined proven or probable IFI as the gold standard. The ideal gold standard to compare the biomarker would be a positive culture of a fungal organism from blood or infected tissue. However, there are significant challenges to establish the presence of fungal infection based on just the isolation of the fungal organism itself. Certain molds such as *Aspergillus* do not grow routinely in blood cultures, the ability to obtain tissue for culture can be impacted by the size and location of a visceral lesion, and the clinical status of a patient may preclude invasive procedures to obtain cultures. Therefore, an alternate endpoint to identify all patients who truly have IFI is necessary. This issue has been addressed by the EORTC/MSG. This group of experts initially created criteria based on clinical, radiographic and culture data to define possible, probable and proven IFI in 2002 and revised these criteria in 2008.^{31,67} These criteria have served as the primary endpoint for major trials of antifungal drug efficacy, in strategy trials, for formulating clinical practice guidelines, as well as for undertaking epidemiologic studies. Consistent use of these criteria as the primary endpoint will allow for comparison of our resultant data to prior and future studies.

13.8 Factors Resulting in False Positive Results

A number of medications, medical interventions, and infections have been suggested as possible causes of false positive results for BG testing.⁶⁸⁻⁷⁰ Table 2 lists the potential causes of false positive results reported in the literature. It is anticipated that recipients of a HCT will have reason to be exposed to a number of these medications, infusions and/or medical interventions. Additionally, *Pneumocystis jiroveci* infection is also considered a cause of a “false positive” BG test. Technically this is not a true false positive as the Fungitell Assay is detecting BG from the cell wall of *Pneumocystis jiroveci* as it would for other fungal infections. However, in this instance it is considered a “false positive” as the treatment of choice for this infection is trimethoprim-sulfamethoxazole as opposed to a typical anti-fungal agent. A sensitivity analysis (as described in Section 13.9.4 below) will be performed to investigate the impact of these false positive inducing factors on the operating characteristics of the 2 biomarkers. The starred factors are likely to be the most clinically relevant and thus they will be focused on.

| Table 2. Potential factors resulting in false positive testing for (1→3) beta-D glucan | |
|---|--|
| Medications | *Amoxicillin-clavulanate |
| Infusions | *Intravenous immune globulin Cellulose filters for IV infusion Albumin |
| Medical interventions | Hemodialysis with cellulose filter Gauze packing on serosal Surfaces |
| Other infections | * Pneumocystis jiroveci |

13.9 Statistical Design

13.9.1 Sample Size and Estimated Event Rates:

The parent trial comparing prophylaxis with an azole (fluconazole or voriconazole) to caspofungin in newly diagnosed AML patients anticipates enrollment of at least 280 patients for each arm with a total cohort of approximately 560 patients. As noted above we anticipate enrollment of approximately 400 patients. This will result in 200 patients from each study arm. Consent for testing will be included as a part of the parent trial enrollment, thus significantly limiting the need for additional resources to complete this biomarker study.

The estimated number of probable or proven IFI events for final analyses will vary by study arm. The Fungitell beta-D-glucan Assay has the potential to identify most pathogenic fungi (with the exception of *Mucorales* species and Cryptococci) and thus a majority of the probable or proven IFIs will be considered as true events.

It is challenging to establish an estimate of the event rate for IFI in this patient population as a prospective trial of anti-fungal prophylaxis in pediatric HCT recipients has never been performed. There have been three retrospective pediatric-specific studies that have attempted to define these event rates.^{26,27,55} The cumulative incidence of IFI in these three studies ranged from 8- 13%. It should be noted that these studies varied in follow-up time, in the types of transplants included, in the antifungal prophylaxis utilized and in the definition for IFI used to define the outcome. More recently an adult randomized and double blind controlled trial compared the efficacy of fluconazole prophylaxis to that of voriconazole in HCT recipients.³ Within 180 days from transplantation, 8.1% of patients on fluconazole and 4.6% of patients on voriconazole developed a breakthrough IFI. This patient population had almost no unrelated umbilical cord blood transplant patients making it a much lower risk group for IFI than our proposed patient population.

In the proposed parent trial included patients will be the recipients of allogeneic stem cells (bone marrow, peripheral blood stem cells, or umbilical cord blood). These HCT patients are those at high-risk for an IFI and thus the anticipated incidence rate of IFI may be higher than that reported in the above referenced adult trial. Alternatively, the proposed trial will only follow patients for 100 days from transplantation and thus later onset IFI will not be identifiable. Considering the data presented above and the proposed study parameters, the COG parent trial has conservatively estimated that the IFI incidence rate will be 7% (20 events) in the azole treatment arm and 2% (6 events) in the caspofungin study arm. Because this ancillary study plans to enroll 70% (400 patients) of the parent trial patients over a three-year period the estimated event rates for the azole and caspofungin arms are 14 and 4 respectively (table 3).

| | Total | Azole Arm | Caspofungin Arm |
|------------|-------|-----------|-----------------|
| Number | 400 | 200 | 200 |
| IFI Rate | 4.6% | 7.0% | 2.0% |
| IFI Events | 18 | 14 | 4 |

13.9.2 Sensitivity, Specificity, PPV, and NPV:

The validity of a biomarker is based on whether the study appropriately categorizes patients with and without the illness in question (sensitivity and specificity). Alternatively the validity of a test can be measured by how well the test results predict the presence or absence of the disease (PPV and NPV). Collectively, sensitivity, specificity, PPV, and NPV are often referred to as the test's operating characteristics. Each component of the operating characteristics will be calculated based first on the entire cohort. As indicated in the estimates above, the incidence of is expected to vary between the two study arms. It is well documented that variations in the incidence/prevalence of a disease will impact the operating characteristics of a diagnostic test specifically for the PPV and NPV. Therefore, each assay's sensitivity, specificity, PPV and NPV will also be calculated separately for each study arm.

The operating characteristics for the Fungitell beta-D-glucan Assay will be computed as follows:

- Outcome of all IFI defined as a single positive test for the Fungitell beta-D-glucan Assay as compared to the EORTC/MSG criteria for all proven or probable IFI.

Sensitivity, specificity, PPV and NPV and their accompanying 95% confidence intervals will be calculated using STATA statistical software version 12.0 (College Station, TX). As noted above, these parameters will first be calculated for the entire cohort and then for each study arm separately. A patient with multiple episodes of IFI will only be included in the analyses as a single IFI. As would be expected in the setting of low incidence, we anticipate that the results will show a low PPV and high NPV. This will not be an indication that the assay is not useful. The intended goal of the assay is to identify all patients with IFI at the earliest time point. In order to identify all such patients there will need to be a tolerance for a certain number of false positive results. Thus in this clinical setting the sensitivity of these assays is the most relevant parameter assuming the number of false positive results is not excessive.

13.9.3 Receiver Operator Characteristics Curve:

In addition to understanding the operating characteristics of a diagnostic test at a single defined threshold, it is also important to understand how variations in the test's threshold can alter the test's operating characteristics. The receiver operating characteristics (ROC) curve is a useful approach to illustrate how these operating characteristics will change as the threshold changes. Therefore, a receiver-operating-characteristics (ROC) curve will be generated with a series of sensitivities and specificities derived from various cutoff values. For the Fungitell Assay cutoffs of ≥ 60 , ≥ 80 , ≥ 100 , and ≥ 120 pg/mL will be used to create the ROC. The ROC curve will be displayed graphically (sensitivity vs. 1-specificity) and evaluated numerically (c-statistic). The c-statistic (also referred to as the area under the curve (AUC)) varies from 0.5 to 1.0 and is a measure of the test's ability to discriminate between patients with and without the gold standard diagnosis.²¹ A c-statistic of 0.5 is possible by chance alone while a perfectly discriminating test will result in a c-statistic of 1.0.

Additionally, the ROC curves will be used in an exploratory analysis to identify the threshold for the biomarker assay that optimizes the diagnostic test's sensitivity while maintaining a reasonable specificity. The identified thresholds will be used to categorize each patient as "likely to have IFI" and "not likely to have IFI". Once these 2 sub-groups are defined we will calculate the incidence rates of IFI for each sub-group and compare them. Because the anticipated incidence for IFI may be variable between the two study

arms (those receiving an azole and those receiving caspofungin) this approach will have to be done at the level of each study arm. The incidence rates will be compared statistically using Pearson's Chi-square analysis.

Finally, to further explore the ideal utility and interpretation of each biomarker, serial testing results will be explored. For this analysis the Fungitell beta-D-glucan Assay will be considered positive when a patient has 2 consecutive test results ≥ 80 pg/mL. Operating characteristics and ROC curves will be constructed in a similar manner as discussed above.

13.9.4 Sensitivity Analysis:

Sensitivity analyses will be explored for the reasons expressed in Section 13.7.1 and 13.8. The first sensitivity analysis will attempt to identify the direction and magnitude of the bias resulting from the availability of clinical BG testing performed outside of the ancillary study. Such testing has the potential to change the treating clinician's approach for diagnosing an IFI. It is possible that these test results could result in more or less investigation (e.g. radiologic imaging) to identify an IFI, which could ultimately impact on the incidence of identified IFI. Therefore, in addition to calculating the operating characteristics for all patients enrolled, the same operating characteristics will be calculated after excluding all patients that had at least 1 biomarker test result available to the treating clinician.

The second sensitivity analysis will be performed to explore the impact of the various factors described in Section 13.8 that may contribute to a positive result for the biomarker. False positive results would impact the final interpretation of sensitivity and PPV for each of the assays. However, it is also possible that one of the factors listed in Table 2 is present in a patient that truly has an IFI. Therefore, we plan to still include all patients in the primary analysis for calculation of the assay's operating characteristics. In this sensitivity analysis, we will eliminate all patients with a positive test that correlates in time with at least 1 of the starred factors listed in Table 2.

13.10 **Significance**

Fungal infections continue to be major contributors to morbidity and mortality in children undergoing HCT. Although antifungal prophylaxis in these patients will reduce the frequency of IFI, it will not eliminate the risk of these devastating infections. Early diagnosis and therapeutic modifications are paramount to improving patient outcomes. The Fungitell beta-D-glucan Assay is a potential diagnostic tool that could improve the time to diagnosis of IFI. More definitive data regarding the operating characteristics of these 2 biomarkers interpreted separately and simultaneously in the setting of a large pediatric cohort receiving anti-fungal prophylaxis are necessary. Evaluating the biomarker first as an integrated test will provide valuable information regarding the utility of each test for future pediatric patients being treated under similar circumstances. It is important to realize that the results of this study (either to support or not support the routine clinical use of the biomarker) will have an important impact on the provision of future clinical care. If the results support the biomarker as an adjunctive diagnostic tool for identifying IFI, then clinicians will be better informed on the clinical application of the assay results. However, if the assay does not perform well in identifying IFI, then clinicians will know that this assay is not useful in this clinical scenario and thus will not order the test. This would result in the conservation of finite resources and redirect the focus of researchers to other modalities for diagnosing fungal infections.

